### **6.2.3 Clinical Laboratory Testing**

Clinical laboratory testing will occur at screening, check-in, predose within 2 hours on each dosing day (Days 1, 8, and 15) (for Part B only), 3 days from dosing (Day 4, 11, 18), and at EOS. Clinical laboratory tests will be performed by the PPD Central Laboratory. Blood and urine samples will be collected under fasting conditions and will be prepared using standard procedures. If any concerning trends are seen during study, investigator can order additional testing for safety on PRN basis.

Repeat clinical laboratory tests may be performed at the discretion of the investigator, if necessary, to evaluate inclusion and exclusion criteria or clinical laboratory abnormalities. The clinical laboratory that will perform the tests will provide the reference ranges for all clinical laboratory parameters. Abnormal clinical laboratory values will be flagged as either high or low (or normal or abnormal) based on the reference ranges for each laboratory parameter.

The following clinical laboratory assessments will be performed:

Hematology	Absolute neutrophil count and differential, hematocrit, hemoglobin, mean corpuscular hemoglobin, mean corpuscular hemoglobin concentration, leukocytes-absolute counts and percentages (basophils, eosinophils, lymphocytes, monocytes, neutrophils), mean corpuscular volume, platelet count, red blood cell count, and red cell distribution width
Serum Chemistry	Alanine aminotransferase, albumin, alkaline phosphatase, aspartate aminotransferase, bilirubin (total + indirect and direct fractions), blood urea nitrogen, calcium, carbon dioxide, chloride, creatinine, gamma-glutamyltransferase, globulin, glucose, lactate dehydrogenase, phosphorus, potassium, sodium, total protein, uric acid, and creatine kinase
Urinalysis	Appearance, bilirubin, color, glucose, ketones, leukocytes, reflex microscopy (performed if dipstick is positive for protein or the blood value is 1+ or greater; and includes bacteria, casts, crystals, epithelial cells, red blood cells, and white blood cells), nitrites, occult blood, pH, protein, specific gravity, turbidity, and urobilinogen
Serology	Hepatitis B surface antigen, hepatitis C virus antibody, and human immunodeficiency virus antibody types 1 and 2 (screening only)

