### **7.3.2 Safety Analyses**

Adverse events will be coded by preferred term and system organ class using the latest version of MedDRA. All AE data will be presented in a data listing. TEAEs will be summarized by treatment and overall, as well as by severity, seriousness, and relationship to study drug. Serious

AEs and AEs leading to discontinuation of study drug will also be presented in the data listings and summarized by treatment and overall.

Actual values and changes from baseline for clinical laboratory test results, vital sign measurements, and 12-lead ECG results will be summarized by treatment at each time point using descriptive statistics (number of participants, mean, SD, median, minimum, and maximum). Physical examination findings will be presented in a data listing.

For safety analysis, unless stated otherwise, baseline will be defined as the last nonmissing assessment (including repeat and unscheduled assessments) predose for each period. An overall baseline for by-sequence analysis will be defined as the last value prior to Day 1 dose.

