 - 900 mg plixorafenib + 150 mg cobicistat (Low Fat)

In addition to analysis by Part A and Part B, pooled analysis by treatment may be conducted as exploratory analysis.

All data listings will be sorted by participant number and collection date where applicable.

No algorithm for imputation of missing data will be employed.

For Part A and B, study days are calculated with respect to the first dose date of any study drug as below:

- If the assessment/observation date is on or after the first dose date of any study drug, then
Study Day = Assessment/Observation Date – First Dose Date of any study drug + 1;
- Otherwise,
Study Day = Assessment/Observation Date – First Dose Date of any study drug.

Unless stated otherwise, for safety analysis in Part A and B, baseline will be defined as the last non-missing assessment (including repeat and unscheduled assessments) pre-dose for each period. This may include a post-dose assessment for the previous period (for example, Day 4 assessment of Treatment Period 1 may be considered a baseline assessment for Treatment Period

2 when a subject has no pre-dose assessments for period 2). Unless stated otherwise, baseline for analysis by sequence is defined as the last assessed value prior to dosing on Day 1 of Period 1.

For summaries of safety assessments, if there are repeated measurements at a time point, the first non-missing assessment at that time point will be used in the summary tables.

For summaries of safety assessments, the maximum and minimum postbaseline result (where applicable), will be selected as the highest and lowest result (respectively) collected after baseline, including repeated and unscheduled assessments.

Unscheduled results will not be included in the summary tables by visit, except for determining Baseline or postbaseline minimum and maximum, but will be presented in data listings.

For Part A and B, to compare the post baseline results of the same treatment across different treatment periods, summaries by treatment and timepoint will standardize the visits as follows:

Analysis Visit	Recorded Visit
Baseline	Baseline result as defined above
Day 2	Day 2, Day 9, or Day 16
Day 3	Day 3, Day 10, or Day 17
Day 4	Day 4, Day 11, or Day 18
Day 5	Day 5, Day 12, or Day 19/EOS

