Actual values and change from baseline for hematology and serum chemistry at each time point, and at the maximum and minimum post baseline value will be tabulated by treatment for the safety set.

An additional summary presenting the actual values and change from baseline for hematology and serum chemistry at each time point, and at the maximum and minimum post baseline value, using an alternate definition of baseline will be tabulated. For the summary, baseline will be defined as the last non-missing assessment (including repeat and unscheduled assessment) on or prior to Check-In (Day -1).

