The protocol specified that TEAEs were to be summarized by severity. A protocol clarification letter (dated 15th May 2024) was issued explaining that AEs would be coded via CTCAE v5.0. It was determined that examining TEAEs by CTCAE grade was desired rather than severity. As such, TEAEs will be summarized by CTCAE toxicity grade. Severity will still be included in AE listings.

For laboratory results, to examine the potential of a treatment effect being carried into the next treatment period by using a by period baseline (because the predose assessment may be on Day 4 of the treatment period, while the subsequent period starts on Day 8), an additional summary using a baseline result from before any treatment (as described in [Section 8.2](#)) will be created to evaluate any safety signal masked by inducing a carry over effect.

The protocol specified that ECG analysis will include analysis of the actual visit and change from baseline summarized by treatment at each timepoint. However, examining the schedule of assessments, the ECG assessments have no post baseline assessments (except Day 19/EOS) if the definition of baseline specified in a protocol clarification letter (dated 15th May 2024) and this SAP is used. As such, ECG summaries will instead be presented at each timepoint overall only, not by treatment, using a baseline definition as specified in [Section 8.6](#).

The protocol specified TEAEs were to be summarized by relationship to study drug. For Part B, all TEAEs and treatment-related TEAEs will be summarized respectively.

12. References

Department of Health and Human Services, Food and Drug Administration (DHHS), Center for Drug Evaluation and Research (US). Guidance for industry: Assessing the effects of food on drugs in INDs and NDAs — clinical pharmacology considerations. June 2022. [cited 2024 Jan 25] [12 screens] Available from: <https://www.fda.gov/regulatory-information/search-fda-guidance-documents/assessing-effects-food-drugs-inds-and-ndas-clinical-pharmacology-considerations>

13. Schedule of Assessments

Part A

	Phase	Screening	Check-in	Treatment Period 1					Treatment Period 2					Treatment Period 3				
Procedure ^(a)	Day/Treatment	D-28 to -1	Day -1	D1	D2	D3	D4	D5	D8	D9	D10	D11	D12	D15	D16	D17	D18	D19/EOS
Admission to clinic			X															
Discharge from the clinic/study																		X
Informed consent		X																
Demographics		X																
Serology ^(b)		X																
Serum FSH ^(c)		X																

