 - h) Clinical laboratory testing will occur at screening, check-in, 3 days from dosing (Day 4, 11, 18), and at EOS. If any concerning trends are seen during study, Investigator can order additional testing for safety on PRN basis. Further details on clinical laboratory assessments, including a complete list of assessments, are provided in [Section 8.2](#) and Protocol Section 6.2.3
 - i) Further details are provided in Protocol Section 6.2.3.
 - j) Urine pregnancy test to be done at screening. Serum pregnancy test to be done at check-in, and at EOS.
 - k) Further details on dosing of study treatments are provided in Protocol Section 5.1.
 - l) Further details on the collection of blood samples for PK analysis are provided in Protocol Section 6.1.
 - m) Further details on the collection of urine samples for PK analysis are provided in Protocol Section 6.1.
 - n) Further details on collection and reporting of AEs are provided in Protocol Section 6.2.
 - o) Information regarding prior medications taken by the participant within the 30 days before signing the ICF will be recorded in the participant's eCRF. Details regarding prior and concomitant medications are provided in Protocol Section 5.5.1.

Part B

	Phase	Screening	Check-in	Treatment Period 1					Treatment Period 2					Treatment Period 3				
Procedure ^(a)	Day/Treatment	D-28 to -1	Day -1	D 1	D2	D3	D4	D5	D8	D9	D10	D11	D12	D15	D16	D17	D18	D19/EOS
Admission to clinic			X															
Discharge from the clinic/study																		X
Informed consent		X																
Demographics		X																
Serology ^(b)		X																
Serum FSH ^(c)		X																
Inclusion/exclusion criteria		X	X															
Medical history		X	X															
Height, weight, and BMI ^(d)		X	X	X					X					X				X
Physical examination ^(e)		X	X	X					X					X				X
Vital sign measurements ^(f)		X	X	X	X	X	X	X	X	X	X	X	X	X	X	X	X	X
12-lead ECG ^(g)		X		X					X					X				X
Clinical laboratory testing ^(h)		X	X	X			X		X			X		X			X	X
Urinalysis ^(h)		X	X	X			X		X			X		X			X	X
Urine drug/alcohol/cotinine screen ⁽ⁱ⁾		X	X															
Pregnancy test ^(j)		X	X															X
Sample for pharmacogenomics		X																
Study drug administration ^(k)				X					X					X				
PK sample collection ^(l)				X	X	X	X	X	X	X	X	X	X	X	X	X	X	X
Adverse events ^(m)		X																
Prior/concomitant medications ⁽ⁿ⁾		X																

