Abbreviations: AEs, adverse events; BCRP, breast cancer resistance protein; BMI, body mass index; D, day; ECG, electrocardiogram; EOS, end of study; FSH, follicle-stimulating hormone; PD, pharmacodynamic; P-gp, P-glycoprotein; PK, pharmacokinetic; QTcF, QT interval corrected for heart rate using Fridericia's formula

Notes:

- When procedures are scheduled for the same timepoint ECG should be performed first, followed by vital sign assessment, urine collection, meal, blood collection, and dose (in that order).
- A complete list of serology assessments is provided in [Section 8.2](#).
- Females only. Further details are provided in Protocol Section 6.2.3.

- d) Height and weight will be measured, and BMI calculated at screening only. Only weight will be measured at check-in, dosing, and EOS.
- e) A full physical examination will be performed at screening and check-in. A symptom-driven physical examination may be performed at other times, at the investigator's or designee's discretion. Further details are provided in Protocol Section 6.2.6.
- f) Further details on vital signs (respiratory rate, body temperature, pulse rate, and blood pressure) measurements are provided in Protocol Section 6.2.4.
- g) ECG should be recorded at screening, predose within 2 hours on each dosing day, and at EOS. Further details on ECG recordings are provided in Protocol Section 6.2.5.
- h) Clinical laboratory testing will occur at screening, check-in, predose within 2 hours on each dosing day, 3 days from dosing (Day 4, 11, 18), and at EOS. If any concerning trends are seen during study, the investigator can order additional testing for safety on PRN basis. Further details on clinical laboratory assessments, including a complete list of assessments, are provided in Section 8.2 and Protocol Section 6.2.3.
- i) Further details are provided in Protocol Section 6.2.3.
- j) Urine pregnancy test to be done at screening. Serum pregnancy test to be done at check-in, and at EOS.
- k) Further details on dosing of study treatments are provided in Protocol Section 5.1.
- l) Further details on the collection of blood samples for PK analysis are provided in Protocol Section 6.1.
- m) Further details on collection and reporting of AEs are provided in Protocol Section 6.2.

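### In Part B, the alternate laboratory baseline stops at Day -1, so the Day 1 predose draw can be reported as a post-baseline maximum or minimum in the additional summary

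*SAP*

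**What the plan says.** SAP 8.2 plans two laboratory summaries. The main one uses the by-period baseline of SAP Section 4, the latest available result before dosing in each period. The additional one reports actual values and changes "at each time point, and at the maximum and minimum post baseline value, using an alternate definition of baseline will be tabulated". For it, "baseline will be defined as the last non-missing assessment (including repeat and unscheduled assessment) on or prior to Check-In (Day -1"). The text does not limit this summary to Part A.

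SAP Section 4 defines the extremes for all safety summaries: the maximum and minimum "will be selected as the highest and lowest result (respectively) collected after baseline, including repeated and unscheduled assessments". No clause requires the result to follow a dose.

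The laboratory schedules of the two parts differ. For Part A, the schedule notes in SAP Section 13 say: "Clinical laboratory testing will occur at screening, check-in, 3 days from dosing (Day 4, 11, 18), and at EOS". For Part B, the corresponding note lists "check-in, predose within 2 hours on each dosing day, 3 days from dosing (Day 4, 11, 18), and at EOS". Protocol 6.2.3 gives the same difference: testing takes place "predose within 2 hours on each dosing day (Days 1, 8, and 15) (for Part B only").

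SAP Section 11 gives the reason for the additional table. It wants "an additional summary using a baseline result from before any treatment", so that a signal carried into the next period is not masked by a by-period baseline.

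**The concern.** The Day -1 cut-off fits Part A, where check-in is the last scheduled laboratory draw before any drug. In Part B there is one more pre-drug draw, within 2 hours before the Day 1 dose. Under the alternate definition that draw falls after baseline, and under the Section 4 rule it becomes a candidate for the post-baseline maximum or minimum.

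Two things follow. First, a value taken before any exposure can be shown as a post-baseline extreme. This matters most for ALT, AST and bilirubin, because Protocol 1.3 describes transient rises in these analytes and Protocol 6.2.2.6 makes Grade 2 or higher rises events of special interest. Second, carry-over cannot exist in Period 1, so the two summaries should agree there. In Part B they use different Period 1 baselines, and a reader comparing them could take the difference for carry-over.

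**Working it through.** The plan states no figure on this point, so there is nothing to reproduce. The finding rests on the text, and the arithmetic below only illustrates its size.

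**1. Count the scheduled draws after Day -1** (Protocol 3.3.1 and 3.3.2; SAP Section 13).

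| | Draws after Day -1 | Number | Of which before any drug |
|---|---|---|---|
| Part A | Days 4, 11, 18, 19 | 4 | 0 |
| Part B | Days 1 (predose), 4, 8, 11, 15, 18, 19 | 7 | 1 |

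**2. Share of extremes with no drug effect.** Assume the 7 values for one analyte in one participant are exchangeable and have no ties. Each is then equally likely to be the largest, and equally likely to be the smallest.
- P(Day 1 predose is the maximum) = 1/7 = 14.3%, or 16 × 1/7 = 2.3 of 16 participants per analyte.
- P(it is the minimum) = 1/7 = 14.3%.
- P(it is either) = 2/7 = 28.6%, or 16 × 2/7 = 4.6 of 16.
- With independent participants, P(at least one of 16 has it as the maximum) = 1 − (6/7)^16 = 91.5%.

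**3. Effect on the size of the maximum.** If the draws are also independent and normal, the expected maximum is 1.27 within-participant SD for 6 draws and 1.35 for 7, a difference of 0.085 SD.

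**4. The same with a drug effect.** Let all six post-dose values rise by d SD, with independent normal draws. Then P(Day 1 is the maximum) = ∫ φ(x) Φ(x − d)^6 dx, and P(Day 1 is the minimum) = ∫ φ(x) [1 − Φ(x − d)]^6 dx.

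| d (SD) | Day 1 is maximum | Day 1 is minimum | Added to expected maximum (SD) |
|---|---|---|---|
| 0 | 14.3% | 14.3% | 0.085 |
| 0.5 | 6.7% | 26.1% | 0.034 |
| 1 | 2.7% | 41.4% | 0.012 |
| 2 | 0.3% | 73.3% | 0.001 |

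A rise makes the predose draw a rarer maximum and a more common minimum. A fall does the reverse.

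**5. Difference between the two tables in Period 1.** For a Part B participant with both draws, the Day 4 change from baseline is
- main summary: Y(Day 4) − Y(Day 1 predose);
- additional summary: Y(Day 4) − Y(Day -1).

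The additional summary minus the main one equals Y(Day 1 predose) − Y(Day -1). Both values precede any drug, so this difference contains neither a drug effect nor carry-over.

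**6. After the correction.** With the baseline run up to the first dose, Part B has 6 scheduled post-baseline draws, all after exposure, and the chance of a pre-drug extreme is 0. Part A keeps its 4 scheduled draws and its Day -1 baseline.

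**The case against.** The strongest reply is that little depends on this table. It is additional and descriptive, and no decision rule uses it. The main summary already treats the Part B Day 1 draw as the Period 1 baseline. Every result is listed, flagged and CTCAE-graded (SAP 8.2), and treatment emergence of an adverse event is judged against exposure (SAP 8.1), so a predose rise can be identified. The standardized visits in SAP Section 4 have no Day 1 row, so the by-visit rows would not show the draw. A programmer might also restrict the extremes to post-dose results without being told to. All of this stands and limits the importance of the point. It does not close the gap, because the rule for extremes does not use the visit table and the SAP nowhere states a post-dose restriction.

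A second reply is that Day -1 may be the better baseline. It is one day before dosing, it is scheduled for everyone, and it gives both parts one rule, which may help the exploratory pooling mentioned in SAP Section 4. Also, note (a) to the Part B schedule places the meal before blood collection when procedures coincide, whereas Protocol 6.2.3 asks for fasting laboratory samples. Three of the four Part B sequences (B:D:A, D:B:C, C:A:B) start with a fed treatment, so the Day 1 draw might follow a meal. This has some weight, and those two texts need reconciling. It applies equally to the main table, which already uses that draw, and it gives no reason to count a pre-drug value as a post-baseline extreme.

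A reader might infer three stronger points that the documents do not support:
- **That SAP 8.2 contradicts SAP Section 11.** It does not, since Day -1 is before any treatment.
- **That it contradicts the other first-dose baselines.** Protocol 7.3.2 says "An overall baseline for by-sequence analysis will be defined as the last value prior to Day 1 dose", and SAP Section 4 has a similar rule. Both concern by-sequence analysis, and the SAP 8.6 baseline concerns ECG summaries. The laboratory rule differs from these, but it is labelled an alternate definition for a different table.
- **That the Day 1 draw would supply 1/3 to 1/2 of Period 1 extremes.** That requires a by-treatment or by-period layout, which SAP 8.2 states for the main summary but not for this one.

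**Conclusion.** The point holds for Part B only. Followed literally, SAP 8.2 and SAP Section 4 together allow an untreated Day 1 value to be reported as a post-baseline maximum or minimum in the additional laboratory summary, and they give the two summaries different Period 1 baselines. One of 7 scheduled draws is affected, which means about 14% of maxima and about 14% of minima if there is no drug effect and draws are exchangeable. The documents give no laboratory variability, so these shares are illustrations and not predictions.

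A reader might also infer that the wording could hide a liver signal. It cannot do so through the extremes: one more candidate can only raise a maximum or lower a minimum, and with a 1 SD post-dose rise the predose draw would be the maximum in only about 3% of participants. The risk is an occasional spurious extreme and a misleading comparison between the two tables. This is a minor correction.

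**What to change.** Amend SAP 8.2 in two respects for the additional summary:
1. Take the post-baseline maximum and minimum only from results collected after the first dose of any study drug. This clause alone removes the untreated extremes.
2. Define the alternate baseline as the latest available result, repeats and unscheduled results included, before that first dose, as SAP 8.6 already does for ECG. This uses the closest pre-treatment sample and gives both summaries the same Period 1 baseline.

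While editing, state whether this summary is presented by treatment or overall.

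The cost is a sentence or two of SAP text and the matching programming specification. No new data are needed, and Part A's scheduled draws and baseline do not change.

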8.3. Vital Sign Measurements

Vital signs will include systolic and diastolic blood pressure, pulse rate, respiratory rate, and body temperature, and will be measured at the timepoints indicated in the schedule of assessments (schedules of assessments can be found in [Section 13](#)).

All vital sign measurements will be presented in a data listing. The actual values and change from baseline values at each time point, and at the maximum and minimum post baseline value will be tabulated by treatment for the safety population.

8.4. Physical Measurements

All body weight, height, and BMI measurements will be presented in a data listing.

8.5. Physical Examination

A full physical examination will include, at minimum, assessment of skin, head, ears, eyes, nose, throat, neck, thyroid, lungs, heart, cardiovascular, abdomen, lymph nodes, and musculoskeletal system/extremities. A brief physical examination will include, at minimum, assessment of skin, lungs, cardiovascular system, and abdomen (liver and spleen).

Full physical examinations will be performed at screening and check-in, and a symptom driven physical examinations may be performed at the timepoints indicated in the schedule of assessments (schedules of assessments can be found in [Section 13](#)).

All physical examination results will be presented in a data listing.

8.6. Electrocardiograms

Single 12-lead ECGs will be obtained after the participant has been in the supine position for at least 5 minutes. A single repeat measurement is permitted at screening for eligibility determination. Assessments will include comments on whether the tracings are normal or abnormal, rhythm, presence of arrhythmia or conduction defects, morphology, any evidence of myocardial infarction, or ST-segment, T-Wave, and U-Wave abnormalities.

Heart Rate, RR interval, PR interval, QRS width, QT interval, and QT interval corrected for heart rate using Fridericia's formula (QTcF), and interpretation of ECG will be captured on the eCRF.

Single 12-lead ECG will be performed at the timepoints indicated in the schedule of assessments (schedules of assessments can be found in [Section 13](#)).

All ECG data will be presented in a data listing. The actual values and change from baseline at each time point, and at the maximum and minimum post baseline value, will be tabulated overall for the safety analysis set. For ECG summaries baseline will be defined as the last non-missing assessment (including repeat and unscheduled assessments) prior to the first dose of any study drug.

9. Other Analysis

For the following analysis, the methodology and data handling specifications for this data, if applicable, will be described in a separate analysis document created by the sponsor, *Fore Biotherapeutics*, or their designee.

In Part A only, evaluation of the metabolic profile of plixorafenib in plasma and urine will be conducted and the results will be reported separately.

If feasible, in Part A and B, the possible effect of pharmacogenomic variations on the PK of plixorafenib and/or the effect of cobicistat, including polymorphisms in P-gp, BCRP, and UGT will be evaluated.

In Part B only, the effect of single dose administration of plixorifenib on endogenous biomarkers such as coproporphyrin may be evaluated.

10. Interim Analysis

No formal interim analyses are planned.

As noted in [Section 1](#), analysis was conducted at the end of Part A to facilitate the decision making process for the requirement and design of Part B of the study.

11. Changes in the Planned Analysis

Any changes from this statistical analysis plan will be documented in the CSR for this study.

The protocol specified that TEAEs were to be summarized by severity. A protocol clarification letter (dated 15th May 2024) was issued explaining that AEs would be coded via CTCAE v5.0. It was determined that examining TEAEs by CTCAE grade was desired rather than severity. As such, TEAEs will be summarized by CTCAE toxicity grade. Severity will still be included in AE listings.

For laboratory results, to examine the potential of a treatment effect being carried into the next treatment period by using a by period baseline (because the predose assessment may be on Day 4 of the treatment period, while the subsequent period starts on Day 8), an additional summary using a baseline result from before any treatment (as described in [Section 8.2](#)) will be created to evaluate any safety signal masked by inducing a carry over effect.

The protocol specified that ECG analysis will include analysis of the actual visit and change from baseline summarized by treatment at each timepoint. However, examining the schedule of assessments, the ECG assessments have no post baseline assessments (except Day 19/EOS) if the definition of baseline specified in a protocol clarification letter (dated 15th May 2024) and this SAP is used. As such, ECG summaries will instead be presented at each timepoint overall only, not by treatment, using a baseline definition as specified in [Section 8.6](#).

The protocol specified TEAEs were to be summarized by relationship to study drug. For Part B, all TEAEs and treatment-related TEAEs will be summarized respectively.

12. References

Department of Health and Human Services, Food and Drug Administration (DHHS), Center for Drug Evaluation and Research (US). Guidance for industry: Assessing the effects of food on drugs in INDs and NDAs — clinical pharmacology considerations. June 2022. [cited 2024 Jan 25] [12 screens] Available from: <https://www.fda.gov/regulatory-information/search-fda-guidance-documents/assessing-effects-food-drugs-inds-and-ndas-clinical-pharmacology-considerations>

13. Schedule of Assessments

Part A

	Phase	Screening	Check-in	Treatment Period 1					Treatment Period 2					Treatment Period 3				
Procedure ^(a)	Day/Treatment	D-28 to -1	Day -1	D1	D2	D3	D4	D5	D8	D9	D10	D11	D12	D15	D16	D17	D18	D19/EOS
Admission to clinic			X															
Discharge from the clinic/study																		X
Informed consent		X																
Demographics		X																
Serology ^(b)		X																
Serum FSH ^(c)		X																
Inclusion/exclusion criteria		X	X															
Medical history		X	X															
Height, weight, and BMI ^(d)		X	X	X					X					X				X
Physical examination ^(e)		X	X	X					X					X				X
Vital sign measurements ^(f)		X	X	X	X	X	X	X	X	X	X	X	X	X	X	X	X	X
12-lead ECG ^(g)		X		X					X					X				X
Clinical laboratory testing ^(h)		X	X				X					X					X	X
Urinalysis ^(h)		X	X				X					X					X	X
Urine drug/alcohol/cotinine screen ⁽ⁱ⁾		X	X															
Pregnancy test ^(j)		X	X															X
Sample for pharmacogenomics		X																
Study drug administration ^(k)				X					X					X				
PK sample collection ^(l)				X	X	X	X	X	X	X	X	X	X	X	X	X	X	X
Urine PK sample collection ^(m)				X	X				X	X				X	X			
Adverse events ⁽ⁿ⁾									X									
Prior/concomitant medications ^(o)									X									

Abbreviations: AEs, adverse events; BCRP, breast cancer resistance protein; BMI, body mass index; D, day; ECG, electrocardiogram; EOS, end of study; FSH, follicle-stimulating hormone; PD, pharmacodynamic; P-gp, P-glycoprotein; PK, pharmacokinetic; QTcF, QT interval corrected for heart rate using Fridericia's formula

Notes:

- a) Ideal procedural flow for site will be ECG → vital signs → meal (for treatment 3) → blood collection → dosing. When procedures overlap or occur at the same time point, all blood draws should follow vital signs or ECGs, and PK sampling should be timed to occur last and as close

- to the scheduled time window as possible. When procedures are scheduled for the same timepoint ECG should be performed first, followed by vital sign assessment, urine collection, meal, blood collection, and dose (in that order).
- b) A complete list of serology assessments is provided in [Section 8.2](#).
 - c) Females only. Further details are provided in Protocol Section 6.2.3.
 - d) Height and weight will be measured, and BMI calculated at screening only. Only weight will be measured at check-in, dosing, and EOS.
 - e) A full physical examination will be performed at screening and check-in. A symptom-driven physical examination may be performed at other times, at the investigator's or designee's discretion.
 - f) Further details on vital signs (respiratory rate, body temperature, pulse rate, and blood pressure) measurements are provided in Protocol Section 6.2.4.
 - g) ECG should be recorded at screening, pre-dose within 2 hours on each dosing day, and at EOS. Further details on ECG recordings are provided in Protocol Section 6.2.5.
 - h) Clinical laboratory testing will occur at screening, check-in, 3 days from dosing (Day 4, 11, 18), and at EOS. If any concerning trends are seen during study, Investigator can order additional testing for safety on PRN basis. Further details on clinical laboratory assessments, including a complete list of assessments, are provided in [Section 8.2](#) and Protocol Section 6.2.3
 - i) Further details are provided in Protocol Section 6.2.3.
 - j) Urine pregnancy test to be done at screening. Serum pregnancy test to be done at check-in, and at EOS.
 - k) Further details on dosing of study treatments are provided in Protocol Section 5.1.
 - l) Further details on the collection of blood samples for PK analysis are provided in Protocol Section 6.1.
 - m) Further details on the collection of urine samples for PK analysis are provided in Protocol Section 6.1.
 - n) Further details on collection and reporting of AEs are provided in Protocol Section 6.2.
 - o) Information regarding prior medications taken by the participant within the 30 days before signing the ICF will be recorded in the participant's eCRF. Details regarding prior and concomitant medications are provided in Protocol Section 5.5.1.

Part B

	Phase	Screening	Check-in	Treatment Period 1					Treatment Period 2					Treatment Period 3				
Procedure ^(a)	Day/Treatment	D-28 to -1	Day -1	D 1	D2	D3	D4	D5	D8	D9	D10	D11	D12	D15	D16	D17	D18	D19/EOS
Admission to clinic			X															
Discharge from the clinic/study																		X
Informed consent		X																
Demographics		X																
Serology ^(b)		X																
Serum FSH ^(c)		X																
Inclusion/exclusion criteria		X	X															
Medical history		X	X															
Height, weight, and BMI ^(d)		X	X	X					X					X				X
Physical examination ^(e)		X	X	X					X					X				X
Vital sign measurements ^(f)		X	X	X	X	X	X	X	X	X	X	X	X	X	X	X	X	X
12-lead ECG ^(g)		X		X					X					X				X
Clinical laboratory testing ^(h)		X	X	X			X		X			X		X			X	X
Urinalysis ^(h)		X	X	X			X		X			X		X			X	X
Urine drug/alcohol/cotinine screen ⁽ⁱ⁾		X	X															
Pregnancy test ^(j)		X	X															X
Sample for pharmacogenomics		X																
Study drug administration ^(k)				X					X					X				
PK sample collection ^(l)				X	X	X	X	X	X	X	X	X	X	X	X	X	X	X
Adverse events ^(m)		X																
Prior/concomitant medications ⁽ⁿ⁾		X																

Abbreviations: AEs, adverse events; BCRP, breast cancer resistance protein; BMI, body mass index; D, day; ECG, electrocardiogram; EOS, end of study; FSH, follicle-stimulating hormone; PD, pharmacodynamic; P-gp, P-glycoprotein; PK, pharmacokinetic; QTcF, QT interval corrected for heart rate using Fridericia's formula

Notes:

- When procedures are scheduled for the same timepoint ECG should be performed first, followed by vital sign assessment, urine collection, meal, blood collection, and dose (in that order).
- A complete list of serology assessments is provided in [Section 8.2](#).
- Females only. Further details are provided in Protocol Section 6.2.3.

- d) Height and weight will be measured, and BMI calculated at screening only. Only weight will be measured at check-in, dosing, and EOS.
- e) A full physical examination will be performed at screening and check-in. A symptom-driven physical examination may be performed at other times, at the investigator's or designee's discretion. Further details are provided in Protocol Section 6.2.6.
- f) Further details on vital signs (respiratory rate, body temperature, pulse rate, and blood pressure) measurements are provided in Protocol Section 6.2.4.
- g) ECG should be recorded at screening, predose within 2 hours on each dosing day, and at EOS. Further details on ECG recordings are provided in Protocol Section 6.2.5.
- h) Clinical laboratory testing will occur at screening, check-in, predose within 2 hours on each dosing day, 3 days from dosing (Day 4, 11, 18), and at EOS. If any concerning trends are seen during study, the investigator can order additional testing for safety on PRN basis. Further details on clinical laboratory assessments, including a complete list of assessments, are provided in Section 8.2 and Protocol Section 6.2.3.
- i) Further details are provided in Protocol Section 6.2.3.
- j) Urine pregnancy test to be done at screening. Serum pregnancy test to be done at check-in, and at EOS.
- k) Further details on dosing of study treatments are provided in Protocol Section 5.1.
- l) Further details on the collection of blood samples for PK analysis are provided in Protocol Section 6.1.
- m) Further details on collection and reporting of AEs are provided in Protocol Section 6.2.
